1.0 Background

Every year smoking kills almost 500,000 Americans and costs the nation 1.6% of the gross domestic product. [1] Over 20 million U.S. smokers attempt to quit smoking annually, yet two-thirds or more are not treated with proven cessation medications. [2, 3] When medication is provided, it is not biologically tailored. Metabolism Informed Smoking Treatment (MIST) increases precision of smoking treatment by leveraging speed of nicotine metabolism to optimize pharmacotherapy.

MIST matches the right patient to the right drug. MIST seeks to overcome one of the most serious limitations of the current standard of care for smoking treatment, which is the generic (i.e., non-biologically tailored) nature of medication selection. [4] About 60% of smokers are "normal" (i.e., faster) metabolizers of nicotine for whom nicotine replacement therapy (NRT) produces sub-optimal results. [5] Yet about 90% of all smokers who use cessation medication use nicotine replacement, resulting in widespread therapeutic mismatch. [2] For these "normal" metabolizers, Varenicline shows evidence of improved quit rates over NRT among normal, but not slow, metabolizers. [5]

The nicotine metabolite ratio -- NMR --is a validated, reproducible biomarker for nicotine metabolism. A large body of research has established the nicotine metabolite ratio (NMR) as a validated biomarker of nicotine metabolism that predicts smoking behavior and therapeutic response to cessation pharmacotherapy. Measurements of plasma NMR are reliable across analytical methods and laboratory sites, unaffected by sampling time or storage temperature, and for regular daily smokers, are consistent despite variation in smoking. [6-8] Finally, NMR reflects both genetic and environmental influences on nicotine metabolism, and therefore may have even greater predictive power than genetic markers. [9]

NMR is associated with smoking-related traits and overall treatment response. Fast/normal (i.e., higher NMR) vs. slower metabolizers smoke more cigarettes per day, [10-12] smoke more intensely, [13] exhibit enhanced abstinenceinduced neural responses to smoking cues in craving-specific brain regions, [14] and have greater thalamic nicotinic receptor availability in early abstinence. [15]

Collectively, these metabolism-associated physiologic differences explain in part why fast/normal metabolizers have greater difficulty in quitting and consistently have the lower quit rates at end-of-treatment. [16-18]

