Informed by our preliminary data, we propose a scientifically rigorous RCT design of approximately 1,000 adult CMS beneficiaries or those with prescription coverage, who are daily smokers hospitalized at Vanderbilt University Medical Center (VUMC) to compare effects of MIST vs. UC on: abstinence (1° aim), implementation in clinical practice (2° aim), and health care utilization and mortality (exploratory). All participants will receive UC for tobacco treatment, including: (1) bedside tobacco consult; (2) a prescription for varenicline or NRT; and (3) automated phone calls via TelASK to promote engagement after study enrollment. Medication prescriptions will be NMR-guided for MIST participants and patient-provider selected for UC participants. Type of NRT (e.g., inhaler, gum, patch, etc.) will be informed by insurance type. For example, some plans in Medicare Part D cover only prescription NRT (inhaler, nasal spray) while most state Medicaid programs only cover over-thecounter (OTC) meds (e.g., patch, gum, lozenge). The research team will work with PCPs and their staff to facilitate smoking treatment after study enrollment and will track pharmacy records for PCP-generated prescriptions for patients who continue smoking. PCPs of patients in MIST will be given the NMR results, while PCPs of UC participants will not. Phone surveys will be conducted at approximately 1, 3, 6, and 12 months to assess medication adherence and smoking status, with biochemical validation of abstinence at 6 and 12 months via salivary cotinine for those not using nicotine-containing products at the time of testing. For those using nicotinecontaining products at the time of testing, carbon monoxide or anabasine (if available) will be used. See Table 2 for cut-off values. If feasible within the study timeline and staffing, health care utilization and mortality will be tracked passively over 12 months via existing databases (e.g., Tennessee Hospital Discharge Data System, TN HDDS) via exploratory Aim 3. Investigators have complementary and broad expertise to conduct MIST, the first large RCT to incorporate NMR results into clinical treatment of smoking.

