 - If the main consent process takes place remotely, the consenting structure will remain the same (i.e. screening consent will be completed prior to the main consent). In this case, study staff will electronically provide a copy of all applicable study documents to the patient prior to verbally reviewing all elements of the consent. If no electronic delivery of the main consent is possible, a paper copy of the main consent will be provided in-person or mailed to the patient before verbal review over the phone.
 - Baseline survey may be completed remotely, as needed, due to the time constraints of meeting participants in-person.
 - Participants will be compensated with \$10 for the screening blood draw and \$40 for completion of the baseline survey.

- Randomization
 - Randomization will take place after a valid NMR has resulted. As noted above, in the case that a participant meets all other criteria, but NMR is not resulted, a patient may be consented but will not be randomized until after the NMR is resulted.
 - In the rare event that an NMR sample results as invalid (nicotine unable to be detected in sample) after the participant has been enrolled, the study team will obtain a backup sample within approximately a week of study enrollment. This sample will either be a stored clinical sample or the study team will coordinate a new blood draw. As needed, a courier service will be used to retrieve and deliver this sample.
 - Study medication will be provided by a VUMC or outside pharmacy after study enrollment either in-person or mailed to the participant's home. Participants who are unable to pay for their insurance co-pays for smoking cessation medication may be referred to existing programs at Vanderbilt University Medical Center to facilitate obtaining medication. In the infrequent instance where charges related to the study are mistakenly billed to the participant, the study team will reimburse the participant via a gift card.
 - Participant will be provided with study information including a copy of the consent document and, for those randomized to the MIST arm, information on the NMR test.

2. Post-enrollment treatment support

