5.3 Inclusion Criteria

Inclusion Criteria

- 18 years old or older
- be enrolled in or pending approval for an insurance plan that supports prescription coverage for smoking cessation medication (including Medicare part D, Medicaid, private insurance, Federal or other governmental, or other insurance) or willing and able to purchase smoking cessation medication and pay for healthcare out of pocket to facilitate delivery of medications
- have a regular provider/PCP or have access to a free or low cost clinic for regular clinical care that can prescribe smoking cessation medication; if patient does not have a PCP, the study team may collaborate with the patient to establish a primary care provider
- agree to quit or try to quit smoking upon study enrollment
- be a daily smoker when smoking normally during the month prior to entering the study
- be medically eligible to use varenicline*
- be medically eligible to use nicotine replacement therapy **
- have received medication recommendations from a tobacco counselor
- agree to take smoking cessation medication (i.e., varenicline OR nicotine replacement therapy) home and consider using it
- have a cell phone or landline that can be reached directly (i.e., without transfer)
- have a permanent address where they live and can receive mail
- estimated life expectancy of at least one year or greater

*Medical eligibility to take varenicline is defined by absence of the following:

- Serious brain condition that impairs cognition (including but not limited to dementia, delirium, brain tumors/metastases, uncontrolled seizures (i.e., seizures within the past 3 mo.))
- pregnancy/planning to become pregnant/breastfeeding in the next year
- history of allergic reaction to varenicline
- unstable/uncontrolled mental health condition:
 - a. altered mental status (e.g., delirium, hallucinations) **OR**
 - b. serious psychiatric symptoms in the past 6 months as defined by suicidal ideation or attempt, hospitalization or ED visit involving a psychiatric condition (e.g., depression, anxiety, bipolar, schizophrenia, schizoaffective disorder, PTSD, substance use (e.g., overdose, other related) **OR**
 - c. changes in psychiatric medication within the past 3 months
- if alcohol use; history of blackouts or seizures with drinking

** Medical eligibility to use nicotine replacement therapy is defined by absence of the following:

- o unstable from cardiovascular perspective

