5.8 Randomization

Patients can be randomized into the study once the NMR test has resulted. Randomization will be stratified on three factors: (1) primary admitting diagnosis (cardiac vs. other); (2) cigarettes/day (≥10, <10); (3) primary insurance (Medicaid, Medicare with Part D, Private Insurance, Federal/Other Governmental/Other Insurance); and (4) NMR status ("normal"/"slow") to ensure that the treatment groups are balanced. After the patient enrolls, the RA will be directed to the electronic randomization screen in REDCap, which, once submitted, automatically assigns the participant to a randomization group.

Blinding: The nature of the study precludes blinding of patients or research staff to the study condition.

Participants will receive a handout describing their assigned treatment. For those randomized to the MIST (precision) arm, the handout will include information on the NMR result and recommended medication. In the event that a participant is enrolled before a valid NMR result is received, study staff may contact the participant via phone/text/email (per participant preference) to notify of randomization status and initiate post-randomization procedures including facilitation of smoking cessation medication. Those randomized to the Usual Care arm will receive their NMR result at study completion, 12 months post-study enrollment; participants in the Usual Care arm who withdraw from the study will not be provided precision care information.

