9.0 Statistical Considerations

9.1 Aim 1

The primary study outcome is biochemically-verified self-reported 7-day point prevalence abstinence at 6 months as defined by salivary cotinine level < 10 ng/ml or expired CO <10 ppm. A secondary outcome is biochemically-verified self-reported 7-day point prevalence abstinence at 12 months. Brief surveys will be conducted at 6 and 12 months after study enrollment to determine self-reported abstinence. Biochemical validation of smoking status is accomplished via mailed salivary cotinine samples or expired CO.

Analysis:

The effect of MIST vs. UC on biochemically-verified abstinence at 6 months will be estimated via a relative risk of abstinence and tested at a 5% significance level via a chi-squared test with Yates' continuity correction. The same method will be applied

to the secondary outcome at 12 months. Anticipated loss to follow up is accounted for in the expected approximate UC abstinence rates where persons lost to follow up will be treated as non-abstinent. However, sensitivity analyses will consider a range of possible odds ratios (1, 2, and 5) linking loss to follow-up and smoking. [51] Exploratory analyses testing for effect heterogeneity will use multivariate logistic regression models adjusting for the main effect of a potential modifier and testing for an interaction with the effect of MIST. The potential effect modifiers to be explored are age, race, sex, NMR, and pre-intervention plan to quit.

Power:

Conservatively assuming a biochemically validated abstinence rate of 10% under UC, a chi-squared test on 1000 patients (at 6 months) will detect a MIST abstinence rate of 16.2% (Risk Difference=6.2%, Relative Risk=1.62, Odds Ratio=1.74) with 80% power. Assuming a 15% biochemically validated abstinence rate under UC (at 12 months), a 22.2% rate under MIST (RD=7.2%, RR=1.48, OR=1.62) is detectable with 80% power. Power was estimated via simulating 20K datasets under the settings above in the statistical program R and were checked against the simplified estimates of the pwr package.

9.2 Aim 2

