A secondary outcome is participant self-reported medication adherence assessed at the 1- and 3-month surveys (Aim 2a). Another secondary outcome is PCP prescriptions for smoking cessation medication after study enrollment for participants who continue to smoke. Pharmacy data from CMS will also be used to supplement participant's self-report of whether they received smoking cessation medication prescriptions from their PCP after study enrollment (Aim 2b) and whether the prescriptions were matched to NMR (Aim 2c).

Analysis:

To account for the longitudinal structure of the data with observations at months 1, 3, 6, and 12, Aim 2 analyses will utilize general estimating equations (GEE) with an autoregressive (AR1) correlation structure adjusting for self-reported smoking status and age, race/ethnicity, education, and dependence (baseline FTND score) in a multivariate logistic GEE model. Each of the following three models will estimate a common odds ratio for MIST vs UC for the outcome of interest. All patients will be included in the analyses and missing covariate data will be multiply imputed via predictive mean matching imputation. Standard errors will be estimated via Rubin's rules and statistical significance tested via Wald tests. Unobserved adherence status or prescriptions will be treated as non-adherent or not received, respectively. H2a: We will estimate the odds ratio for being adherent in the 3 months post-enrollment. H2b: We will estimate the odds ratio for receiving a PCP prescription for a smoking cessation medication in the 12 months post-enrollment. PCP prescriptions occurring between any two time points, e.g. months 3 and 6, will be attributed to the latter time point for analysis. H2c: We will estimate the odds ratio for receiving an NMR-

matching PCP prescription. Exploratory and sensitivity analyses: For each of the three outcomes, exploratory analyses will test for interactions between the MIST effect and month of follow up; and for interactions between the MIST effect and medication type (NRT or varenicline). Sensitivity analyses will vary the correlation structure assumptions to ensure the main conclusions are robust to model specifications.

Power:

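### The exploratory Aim 2 interaction uses medication type, which the randomised arm affects as the plan is written; baseline NMR status is the modifier that randomisation protects

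*Combined protocol and SAP*

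**What the plan says.** Section 9.2 specifies logistic GEE models for self-reported adherence (H2a), a PCP prescription (H2b) and an NMR-matched PCP prescription (H2c). For all three, exploratory analyses will test "for interactions between the MIST effect and medication type (NRT or varenicline". The section does not say whether medication type is the drug recommended, first prescribed, supplied, taken or later prescribed by the PCP, or at what time it is read. The models are described as "adjusting for self-reported smoking status and age, race/ethnicity, education, and dependence (baseline FTND score"; NMR is neither a covariate nor a modifier.

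On how the drug is chosen, section 2.1 states: "Medication prescriptions will be NMR-guided for MIST participants and patient-provider selected for UC participants". Section 5.8 places the MIST drug recommendation after allocation: "For those randomized to the MIST (precision) arm, the handout will include information on the NMR result and recommended medication". Section 4.0 adds: "Study medication will be provided by a VUMC or outside pharmacy after study enrollment".

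One drug-related item does come before randomisation. Section 5.3 requires that patients "have received medication recommendations from a tobacco counselor".

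Section 9.1 handles effect modification differently: "The potential effect modifiers to be explored are age, race, sex, NMR, and pre-intervention plan to quit". Section 9.3 reuses that list for Aim 3.

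**The concern.** A subgroup or interaction analysis keeps the protection of randomisation only if the modifier is fixed before allocation or cannot be changed by it. Drug choice is the thing MIST is meant to change. Within varenicline users, MIST patients are there largely because they are normal metabolizers, while UC patients are there because they and their provider preferred that drug. The same applies in reverse within NRT. Each within-drug comparison of MIST with UC therefore compares groups selected by different rules.

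The result could be reported as MIST helping adherence or uptake with one drug and not the other, when it partly reflects who ended up on each drug. Section 2.1 reports more side effects among slow metabolizers in the earlier trial, so a link between NMR and adherence is plausible, though the protocol does not quantify one. Meanwhile the question that randomisation can answer, whether the MIST effect differs between normal and slow metabolizers, is planned for Aims 1 and 3 and not for Aim 2.

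**Working it through.** **The plan's own figures.** No power or effect size is given for this interaction. The nearest figure is the H2a main effect (50% vs 59.0%, 1000 patients, 80% power). Assuming 1:1 allocation and a two-sided 5% test, I get 81.6% without continuity correction, 79.9% with it, and 80.4% by simulation with Yates' correction. That figure reproduces, but it does not bear on the interaction.

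**Inputs for the NMR mix.**
- Share of normal metabolizers, q: 60% (section 1.0) to 2/3 (section 2.1).
- Pilot NMR-drug matching: 36/43 = 84% intervention, 21/36 = 58% control; varenicline about 60% in both arms (section 3.0).
- Assumed: every patient is on one of the two drugs, and MIST matching is 84% in both NMR groups.

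**MIST.** Varenicline share = 0.84q + 0.16(1-q). Normal share among varenicline users = 0.84q / varenicline share; among NRT users = 0.16q / (1 - varenicline share).
- q = 0.60: varenicline share 0.504 + 0.064 = 0.568; normal share 0.504/0.568 = 0.887 and 0.096/0.432 = 0.222.
- q = 2/3: varenicline share 0.560 + 0.053 = 0.613; normal share 0.560/0.613 = 0.913 and 0.107/0.387 = 0.276.

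**UC.** Let a and b be the probabilities of varenicline in normal and slow metabolizers. Solve qa + (1-q)b = 0.60 and qa + (1-q)(1-b) = 0.58. Subtracting gives (1-q)(2b-1) = 0.02.
- q = 0.60: b = 0.525, a = 0.650; normal share 0.390/0.600 = 0.650 (varenicline) and 0.210/0.400 = 0.525 (NRT).
- q = 2/3: b = 0.530, a = 0.635; normal share 0.423/0.600 = 0.706 and 0.243/0.400 = 0.608.

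| Normal metabolizers among | MIST | UC | Difference |
|---|---|---|---|
| Varenicline users | 89-91% | 65-71% | 21-24 points |
| NRT users | 22-28% | 53-61% | 30-33 points |

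**Sensitivity of the mix.** Suppose equal matching is dropped and MIST is instead solved from 84% matching and 60% varenicline, so that (1-q)(2b-1) = 0.60 - 0.84 = -0.24. The MIST shares become 87-92% and 20-28%. The 95% Wilson interval for 36/43 is about 70-92%. At 70% matching in both groups the MIST varenicline figures are 0.42/(0.42 + 0.12) = 78% (q = 0.60) and 0.467/(0.467 + 0.100) = 82% (q = 2/3). The NRT figures are 0.18/(0.18 + 0.28) = 39% and 0.200/(0.200 + 0.233) = 46%. Against the same UC values the imbalance is smaller but still present.

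**What imbalance could do to the test.** This is an illustration on assumed values. Let adherence average 50% and depend on NMR only, with no effect of arm or drug, 500 patients per arm, one time point and an unadjusted Wald test. Take q = 0.60 and slow metabolizers 10 points more adherent (56% vs 46%). Expected adherence on varenicline is 0.887(0.46) + 0.113(0.56) = 0.471 in MIST and 0.495 in UC, an odds ratio of 0.91. On NRT it is 0.538 and 0.508, an odds ratio of 1.13. The false interaction ratio is 0.91/1.13 = 0.81. If the gap runs the other way, the ratio inverts.

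| Assumed adherence gap (points) | 0 | 5 | 10 | 15 |
|---|---|---|---|---|
| False interaction ratio, 84% matching | 1.00 | 0.90 | 0.81 | 0.72 |
| Rejection at nominal 5%, 84% matching | 5% | 7% | 13% | 24% |
| Rejection at nominal 5%, perfect matching | 5% | 10% | 27-28% | 53-54% |

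**What the undefined term implies for H2b and H2c.**
- If medication type is the PCP-prescribed drug, a patient with no PCP prescription has no value. Everyone who can be classified has then had the H2b event at some point, which does not fit the statement in 9.2 that all patients enter the analyses. Section 5.9 counts a match as a fast metabolizer prescribed varenicline or a slow metabolizer prescribed NRT, so within one prescribed drug the H2c outcome is simply NMR status.
- If it is the initial drug, the PCP may later prescribe either drug or none. Both problems then fall away, and the confounding described above remains.

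**The case against.** The strongest case on the other side has four parts.

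- **The analysis is exploratory.** No primary or main Aim 2 estimate depends on it, and section 9.3 commits to reporting analyses under their planned labels. This stands and limits the weight of the point. The label does not make a within-drug comparison interpretable, however.
- **A baseline version of medication type may exist.** The counselor's recommendation is an eligibility condition, so a reader should not infer that every drug-related value arises after allocation. This also stands, and it offers an alternative fix. But 9.2 does not say that this is the variable meant.
- **Imbalance is not bias.** The figures show different NMR mixes, drawn from a small pilot. With no NMR-outcome relation there is no bias through NMR, and the documents do not give that relation. This stands for size. Other reasons behind drug choice in UC could still confound the comparison.
- **MIST guides the prescription and does not fix it.** A reader might infer that MIST assigns the drug outright, leaving its drug groups purely normal or purely slow. The documents speak of guidance and recommendation, and pilot matching was 84%. The imbalance remains sizeable at that rate.

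It is also tempting to call the H2c interaction circular in all cases. That holds only if medication type is the PCP-prescribed drug. Section 2.1 gives every participant a prescription for one of the two drugs as part of usual care, so the initial drug is an equally natural reading.

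**Conclusion.** The point holds for the exploratory MIST-by-medication-type interaction in section 9.2. As written, the modifier is undefined and is affected by arm, so randomisation does not protect the comparison of MIST with UC within a drug. The differences in normal-metabolizer share, 21-24 points among varenicline users and 30-33 among NRT users, rest on the pilot's match and varenicline rates, a normal share of 60% to 2/3, and equal matching in both MIST NMR groups.

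The bias itself is of unknown size. The illustrative rejection rates rest on assumed adherence gaps and are not a forecast. The two further defects, an undefined value for H2b and an outcome equal to NMR status for H2c, apply only under the PCP-prescribed reading. A reader might go on to doubt the main Aim 2 odds ratios or the primary abstinence result; nothing here supports that, because neither uses medication type.

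**What to change.** In section 9.2, replace medication type with baseline NMR status (normal/slow, as used in the randomisation strata) as the modifier for H2a, H2b and H2c, with all randomised participants included. Report outcomes by drug only in descriptive tables labelled as non-randomised comparisons, stating which drug record they use.

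If an interaction by drug is still wanted, define medication type as the counselor's recommendation recorded before randomisation, and state how a recommendation covering both drugs is classified.

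The cost is one sentence and one model term. A valid NMR is required before randomisation, is a stratification factor, and is already a modifier for Aims 1 and 3, so no new data are needed. What is lost is the formal interaction test by drug received; the by-drug results themselves are kept as description.
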